CM intervention: Through the experience and feedback from the three successful CM groups we will adapt the CBCT-Vet([name] et al., 2017) intervention for use in older adults with anxiety or depressive symptoms. This adaptation will be conducted with input from [name] and [name] (developers of CBCT® and consultants for the proposed project), and the experience and expertise of the study team. Expected adaptations include changing the focus of examples from PTSD to anxiety and depression, as well as adjustments for appropriate use with older Veterans. The CBCT-Vet includes 10 90-minute sessions that will be led by [name], a VA Staff Psychologist and Co-Investigator on the proposed project, who is certified in CBCT® with significant experience in administering CBCT-Vet. Sessions 1 - 4 assist participants in basic mindfulness breathing practices; sessions 4 - 8 focus on personal analysis of factors underlying difficulties with compassion for self or others; the final two sessions (9 and 10) review content and assist with relapse prevention. Session by session topics are: (1) Introduction and learning breathing meditation, (2) Focused attention, (3) Creating space, (4) Mindful awareness, (5) Re-engaging with heroic spirit, (6) Seeing ourselves in others, (7) Appreciation and gratitude, (8) Empathy and engaged compassion, (9) "Putting it all together," and (10) "Putting it all together 2."

Our target is to have 5-8 participants completing each 10-week intervention, thus we will enroll up to 10 per group to account for possible attrition. Two or three of the CBCT-Vet groups (depending on the degree of modification needed based on the initial group) will be conducted sequentially, such that information in the first group can be used to adapt the manualized intervention for the next group.

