Descriptive statistics will be used to summarize the variables as well as to detect outliers and data entry errors. When applicable, normality of the distribution will be examined for outcome variables and residuals of regression model with a normal probability plot. The present project is intended as a feasibility study that will inform, support, and guide development of a subsequent larger-scale VA Merit Award project. Therefore, the primary analysis will be descriptive rather than hypothesis testing. Since the interventions are delivered by group (8-10 participants per group), it is possible that measured or unmeasured characteristics of the participants in a given group or their interactions may affect psychological response to the intervention, attendance, and study outcomes. The analysis plan described below is based on no cluster effect of class. But we will assess the impact of clustering effects by fitting a random effects model for each outcome, and, if necessary, a random class effect will be included in the model to account for the correlations between the individuals in the same class. The intraclass correlation coefficient (ICC) will also be estimated to understand the correlation within class and provide advice for sample size adjustment in future studies.

Will older Veterans with psychological distress [anxiety and/or depression] enroll in and complete the proposed CM intervention? What is the completion rate? Do participants adhere to the treatment (complete practice at home)? We will assess the following outcome measures for enrollment, completion, and adherence to treatment:

- 1) $\underline{\it Enrollment\ rate}$ defined as the proportion of consented subjects among all screened and eligible patients;
- 2) Initiation rate defined as the proportion of subjects who initiate the intervention among all consented subjects;
- 3) $\underline{Completion\ rate}$ defined as the proportion of subjects who complete 6 or more sessions (out of a total of 10 sessions) of intervention among those who start the intervention;
- 4) Practice time at home defined as average minutes that subjects practice at home each week. The mean (and SD) or percentage will be calculated and the 95% confidence intervals will be estimated for all outcomes.

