The associations between patient characteristics and other clinically important baseline variables with the enrollment, completion and adherence will be assessed using univariate tests (Wilcoxon rank sum test, Kruskal-Wallis test, Fisher's exact test, or Spearman correlation coefficient).

Does CM show promise for improving well-being, symptom severity, and/or positive psychological factors relevant to successful aging? We will evaluate the improvement in depression and anxiety (BSI), social connection (SCS-R), satisfaction with life (SWLS) and positive emotions (mDES) from baseline to post-intervention using a linear random effect model and time will be included as a main effect in the model. The random effects model is suitable for examining changes in outcomes in longitudinal studies. It will include all available data, minimizing the effects of missing data on the analyses.

We will also examine the mean (and SD) change scores for each inflammatory biomarker (hs-CRP, IL-6, and TNF-), as well as the association of these changes with practice time.

Sample size assessment:

The sample size was determined based on practical consideration. Since this is a feasibility study, the goal is to examine the effect size such that it can guide future studies. We plan to enroll a total of approximately 24 to 30 participants for the CM groups (3 groups, 8-10 per group) as well as 10 participants for the healthy aging group. Sample size analyses were focused on the CM group, and performed using statistical package R.

A two-sided type I error of 0.05 was assumed.

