The sample size justification was conducted for assessing the enrollment and completion rates (primary outcomes). We assessed the precision of estimates based on projected sample size. From previous investigations, the estimated enrollment and completion rates are between 0.57 and 0.82. Therefore, we considered a range of rate from 0.60 to 0.90 and estimated the margin of error (half of the width) for the 95% confidence interval of enrollment and completion rates. The margin of error of a 95% confidence interval for a proportion is 1.96*p*(1-p)/(Square-root of n) where n is the estimated sample and p is the estimated rate. If an estimated intervention initiation rate is 0.80, a sample size of 30, 27 and 24 will produce a two-sided 95% confidence interval with a margin of error of 0.058, 0.071 and 0.064, respectively. For an estimated completion rate of 0.60, a sample size of 30, 27 and 24 will produce a two-sided 95% confidence interval with a margin of error of 0.086, 0.091 and 0.096, respectively.

We assessed the power for detecting a significant change in psychological outcomes. With a sample size of 24, 27 and 30, we will have 80% power to detect an effect size of 0.53, 0.56 and 0.60 for the change in outcomes from baseline to post-intervention. These effect sizes are achievable based on previous studies, where we observed an effect size of 0.5 for PHQ-9 (mean = 2.3, SD = 4.6), 0.65 for SCS-R (mean = 6.4, SD = 9.9), 1.4 for SWLS (mean = 9.0, SD = 6.6), 0.53 for mDES positive emotion (mean = 4.8, SD = 9.1), and 5.35 for mDES negative emotions (mean = 7.5, SD = 1.4).

Women and ethnic minorities: Women and ethnic minorities will be included in proportion to their representation of Veterans in the VASDHS and PCMHI program. This proportional sampling plan fosters both feasibility of the study and overall generalizability of findings. We recognize that the issues of anxiety and depression among women Veterans is exceptionally important, but warrants separate studies designed and focused specifically to address the issues of most salience to women Veterans.

Children: No children will be included as the scientific focus of this project is on older Veterans

Temporary COVID-19 Updates*

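### A class ICC from two or three sequential CM classes is too imprecise, and too mixed with manual version and delivery mode, to advise the next trial's sample size

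*Combined protocol and SAP*

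**What the plan says.** The Analytic plan in Section 9 recognises that people taught together may resemble one another: group characteristics or interactions "may affect psychological response to the intervention, attendance, and study outcomes". The base analysis assumes no class effect. Clustering is then checked by "fitting a random effects model for each outcome", with a random class effect added if needed, and the ICC is to be "estimated to understand the correlation within class and provide advice for sample size adjustment in future studies". No precision is given for the ICC. The sentence promising 95% confidence intervals follows the four enrollment, initiation, completion and practice-time outcomes.

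The number of classes is small. Section 9, CM intervention, states: "Two or three of the CBCT-Vet groups (depending on the degree of modification needed based on the initial group) will be conducted sequentially", so that experience in one class can change the manual for the next. The Sample size assessment plans "3 groups, 8-10 per group". The Temporary COVID-19 Updates move the first cohort's remaining sessions to WebEx, with three sessions already held to be reviewed, and make cohorts enrolled during the hold virtual.

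The completion rate is the "proportion of subjects who complete 6 or more sessions (out of a total of 10 sessions) of intervention among those who start the intervention". It is a primary outcome: the Sample size assessment was done for "assessing the enrollment and completion rates (primary outcomes)". The part on post-intervention and withdrawal data reports three withdrawals for lack of devices or WIFI. It does not give their class, whether they had started, or how many sessions they attended.

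**The concern.** An ICC is a ratio of variance components, and the between-class component is estimated from the number of classes, not the number of people. Thirty participants in three classes supply two degrees of freedom for it; two classes supply one. The plan nevertheless gives the estimate a design purpose.

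The classes are also not replicates of one intervention. Each may follow a different version of the manual, and delivery mode may differ too. Those differences would be counted as class variance, although the next trial would presumably use a fixed manual and a settled mode.

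What is at stake is the clustering adjustment in the follow-up trial. A chance value near zero would leave that trial too small; a chance high value would make it needlessly large.

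A lesser matter is that the completion rate may partly reflect access to technology during the hold. That is useful feasibility information, but it has a known cause separate from whether older Veterans accept CM.

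**Working it through.** **Inputs.** Classes k = 2 or 3 (Section 9, CM intervention; 3 in the Sample size assessment). Class size m = 8 to 10 (Sample size assessment). Two-sided 5% level (same place). The documents give no ICC value or ICC precision, so there is no plan figure to reproduce for it. I assume estimates r of 0, 0.05, 0.10 and 0.20.

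**ICC interval.** Balanced one-way random-effects model, normal outcome, exact F-based interval:

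- F = 1 + m·r/(1 − r), with k − 1 and k(m − 1) degrees of freedom
- F_L = F / F(0.975) and F_U = F / F(0.025)
- each limit = (F_x − 1)/(F_x + m − 1)
- design effect = 1 + (m − 1) × ICC, with a negative lower limit set to zero

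Worked case, k = 3, m = 8, r = 0.05:

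- F = 1 + 8 × 0.05/0.95 = 1.421, on 2 and 21 degrees of freedom
- F quantiles 4.420 and 0.02535, so F_L = 0.3215 and F_U = 56.06
- lower limit = (0.3215 − 1)/(0.3215 + 7) = −0.093
- upper limit = (56.06 − 1)/(56.06 + 7) = 0.873
- design effect from 1 to 1 + 7 × 0.873 = 7.11

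| Classes × size | r = 0 | r = 0.05 | r = 0.10 | r = 0.20 | Design effect at r = 0.05 |
|---|---|---|---|---|---|
| 3 × 8 | −0.11 to 0.83 | −0.09 to 0.87 | −0.08 to 0.90 | −0.04 to 0.94 | 1 to 7.1 |
| 3 × 10 | −0.08 to 0.79 | −0.07 to 0.86 | −0.05 to 0.89 | −0.02 to 0.93 | 1 to 8.7 |
| 2 × 8 | −0.12 to 0.99 | −0.11 to 0.99 | −0.10 to 1.00 | −0.07 to 1.00 | 1 to 8.0 |
| 2 × 10 | −0.09 to 0.99 | −0.08 to 0.99 | −0.07 to 1.00 | −0.04 to 1.00 | 1 to 9.9 |

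Entries of 1.00 are rounded from 0.995 to 0.997.

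**How such an estimate behaves.** By simulation (400,000 draws per setting), with a true ICC of 0.05 and 3 classes of 8 to 10, the estimate is zero or negative in 47–49% of studies. Its 95th percentile is 0.29–0.33, and a 5% F test detects the class effect in 11–13%.

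**Completion rate, if the three withdrawals were CM starters.** The plan's margins for a rate of 0.60 at n = 30, 27 and 24 reproduce under its printed formula, 1.96·p(1 − p)/√n: 0.086, 0.091 and 0.096. That formula leaves p(1 − p) outside the square root, which is a separate matter. The standard margin, 1.96·√(p(1 − p)/n), is the one to compare with.

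If the other starters complete at rate p, three certain non-completers lower the overall rate by 3p/n:

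| p | n | Fall 3p/n | Standard margin |
|---|---|---|---|
| 0.60 | 30 | 0.060 | 0.175 |
| 0.60 | 24 | 0.075 | 0.196 |
| 0.80 | 30 | 0.080 | 0.143 |
| 0.80 | 24 | 0.100 | 0.160 |

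The shift is 6 to 10 points, inside sampling error in every row.

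**The case against.** The strongest reply on the ICC is that the plan promises only advice. It does not say that the point estimate alone will size the next trial, and it calls the primary analysis descriptive. A reader might infer a commitment to carry the number straight into a power calculation; the text does not go that far. This stands, and it limits the point to the stated purpose and the missing caution. It does not rescue the purpose, because an interval running from no inflation to a design effect of about 7 or more gives a designer almost nothing to act on. Adding the single healthy aging class does not help much: four classes of 8 still give an upper limit of about 0.70 at an estimate of 0.05, and class would then be mixed with arm.

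On completion the reply is stronger. The definition is unambiguous, since a starter with fewer than six sessions is a non-completer, and the protocol openly reports the three withdrawals and their cause. A reader might infer that the completion rate is wrongly defined or that device access is concealed; neither is so. That the three were first-cohort CM starters is suggested by the move to WebEx but not stated. Anyone who had not started would affect the initiation rate instead.

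A reader might also infer that losing three breaks the class target ("Our target is to have 5-8 participants completing each 10-week intervention"). Three lost from 8 to 10 leaves at most 5 to 7, which is inside that range, and the Analytic plan never makes the target an outcome. Nor is there firm ground for saying that the withdrawals inflate the completion ICC: that needs all three to be starters in one class, which is not documented.

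**Conclusion.** The point holds for the ICC. With two or three classes, the estimate cannot serve the sizing purpose given to it. For assumed estimates of 0 to 0.20, the upper 95% limit is 0.79 to 0.94 with three classes and at least 0.99 with two, so the conclusion does not depend on the value assumed. The intervals rest on equal class sizes and a normally distributed outcome. Apart from precision, class cannot be separated from manual version and perhaps delivery mode.

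This does not argue against checking for clustering or estimating an ICC, and it does not undermine the study's feasibility aims. It should be corrected because guidance for the next trial is the study's stated product.

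The completion matter is a conditional reporting suggestion, not an error in the plan. It depends on facts about three people that the documents do not give, and the expected difference of 6 to 10 points (rates of 0.60 to 0.80, 24 to 30 starters) lies within sampling error.

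**What to change.** In the Analytic plan, keep the clustering assessment and report each ICC with its 95% confidence interval as descriptive. Note that class is mixed with manual version and, where it differs, delivery mode. Replace the sizing purpose with a statement that the point estimate will not be used to size the next trial, which will be planned over a range of ICC values.

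Keep the completion rate as defined. State whether the three technology withdrawals had started CM, and their class and sessions attended. If they had started, show the rate without them beside the defined rate.

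The cost is a changed sentence, an interval for each ICC and, if it applies, one table row. The real downside is that the next trial has no study-specific ICC and must be justified over an assumed range.

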*Virtual Research Sessions and Cisco WebEx: During the COVID-19 administrative hold, ORD-funded grants are not permitted to have in-person study visits (including blood draw) for non-clinically critical research assessments. Therefore, we will conduct Compassion Meditation (CM) group therapy sessions and individual pre- and post-intervention sessions using the VA-approved telehealth technology, "Cisco WebEx." We will use Cisco WebEx to conduct the remaining CM group therapy sessions and post-intervention sessions with the first participant cohort as well as to conduct virtual research sessions with future cohorts that are enrolled during the COVID-19 administrative hold. We will use Cisco WebEx to create digital recordings of the group therapy sessions for training and supervision of the study therapist. The recordings will be stored as digital files on the secure VASDHS R-drive network in the PI's R Drive folder (R: [name]) and will only be accessible to VA IRB-approved study staff. The use of Cisco WebEx to conduct virtual research visits is explained to participants in the new Verbal ICF/Script (see attached "Uploaded Documents").

Cisco WebEx is a subscription-based managed service that connects VA to a fully featured FedRAMP Cloud solution. It offers resources for conferencing, webinars, training, collaboration and more. VA staff can schedule and host conferences with both internal VA users and external participants. It is a PIV-enabled and integrates Single Sign-On (SSO). Only staff that need to host or scheduled a meeting need an account.

All scheduled WebEx meeting links will be emailed to each participant securely via Azure encrypted email one day prior to the scheduled meeting day.

Additional information about Cisco WebEx privacy and security features is included in Sections 9.11 and 27.5.

Prior to the first virtual group session, a member of the study team will assist each participant in using Cisco WebEx to ensure participants are comfortable using the program during the virtual research visits. The study therapist, [name], will also review proper participant etiquette and expectations for the new virtual format. [name] will review the previous 3 therapy sessions materials and ensure the participants are comfortable moving forward in the remaining virtual therapy sessions. During the virtual group sessions, a member of the study team will be available to assist participants with any difficulties they may have.

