**As a result of the COVID-19 administrative hold, 3 participants withdrew from the study because of lack of technology (devices and/or WIFI) necessary for virtual training sessions and data collection. With their permission, we will mail the post-intervention study questionnaires (except MOCA and PHQ-9) to the participants who withdrew from the study in order to obtain important post-intervention and withdrawal data. Participants will be compensated \$75 for their time. Participants will be given a pre-paid and addressed envelope to return their completed questionnaires to the study team at VASDHS. They will be instructed NOT to write any PII or VASI on their questionnaires or return envelope.

Section 9.8 Questionnaires & Surveys

9.8) Provide the name and a reference for questionnaires/surveys that are standard or identify them here and attach a copy of the questionnaire/survey. Questionnaires or surveys that are not clinical standard references must be uploaded. Reference the help link for additional information related to surveys administered to VA personnel and approved platforms for web-based surveys.

10-item version of the Connor-Davidson Resilience Scale (Campbell-Sills & Stein, 2007)

12-item Short Form Health Survey (Ware, Kosinski, & Keller, 1996)

6-item short-form De Jong Gierveld Loneliness Scale (De Jong Gierveld & Van Tilburg, 2006)

4-item Duke Social Interaction Subscale (Landerman et al. 1989)

3-item intervention credibility measure (Borkovec & Nau, 1972)

CAIR Pandemic Impact Questionnaire (CESAMH, 2020)

Center for Epidemiological Studies - Depression Scale (Fowler & Christakis, 2008)

Client Satisfaction Questionnaire (Attkisson & Greenfield, 1994)

Cognitive and Affective Mindfulness Scale - Revised (Feldman et al., 2007)

Generalized Anxiety Disorder scale (Spitzer et al., 2006)

Life Orientation Test - Revised (LOT-R; optimism)(Scheier, Carver, & Bridges, 1994)

Modified Differential Emotions Scale (mDES) (Fredrickson et al., 2003)

Patient Health Questionnaire - 9 item (Kroenke, Spitzer, & Williams, 2001)

San Diego Wisdom Scale (Thomas et al., 2019)

Satisfaction with Life Scale (Diener et al., 1985)

Self-Compassion Scale - Short Form (Raes et al., 2011)

Social Connectedness Scale - Revised (Lee, Draper, & Lee, 2001)

Toronto Empathy Questionnaire (Spreng et al., 2009)

UCLA Loneliness Scale - Third Edition (Russell, 1996)

References for above scales:

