Inclusion criteria: (1) VASDHS patient, (2) current age > 55 years, (3) mild-to-moderate anxiety or depressive symptoms (as defined above) at the time of enrollment, (4) stated intention to attend the 10 group sessions at the scheduled times at the VASDHS in addition to the baseline and follow-up study assessment visits, as well as to complete the outside homework assignments, and (5) provides written informed consent for participation.

Exclusion criteria: (1) No active suicidality/homicidality in the preceding six months, (2) untreated alcohol or substance use disorders (those co-enrolled in the VASDHS Alcohol and Drug Treatment Program will be eligible), (3) changes to psychiatric medications within six months of baseline evaluation (changes to medications during the course of the study will be permitted as determined appropriate by Veteran's treating clinicians, but changes will be recorded to further describe the sample), (4) medical and/or psychiatric instability interfering with current ability to engage in the group sessions and outside homework assignments.

As part of the routine clinical service/care, all Veterans referred to the PCMHI service are screened for depressive symptoms with the PHQ-9, and for anxiety symptoms with the GAD-7. Thus we do not expect screen failures among participants who consent the consent process.

Section 10.6 Avoiding coercion of students or employees

10.6) Indicate how coercion of students and/or employees will be avoided:

Students will not be included.

Employees of the investigators will not be recruited, but other VASDHS employees can be recruited /enrolled.

Section 11 - Recruitment

11) Describe, step-by-step, the plans for recruitment of subjects (or selection of subjects as in record review). This description must include how, when, and where potential subjects are approached as well as procedures for identifying potential participants (through medical records, physician referral, third-party sources, etc.). Include how selection is equitable. Indicate if vulnerability to coercion may be present and if so plans to ensure voluntary participation.

Re	cr	mi	tn	no	n	۲	•
IVE	U	ui	CI.	IIIC		L	٠

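### Should the primary completion rate be redefined or split because the COVID update changed how sessions were delivered?

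*Combined protocol and SAP*

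**What the plan says.** Section 9, Analytic plan, gives this definition of completion: "proportion of subjects who complete 6 or more sessions (out of a total of 10 sessions) of intervention among those who start the intervention". The neighbouring definition, initiation, is the share of consented subjects who begin the intervention. The Sample size assessment names enrollment and completion as the primary outcomes, assumes 24 to 30 CM participants in three groups of 8 to 10, and works its completion example at a rate of 0.60. The lay summary in Section 5 allows as few as 20 CM participants, and the CM intervention text allows two groups.

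The study was designed for attendance on site: inclusion criterion 4 asks for a "stated intention to attend the 10 group sessions at the scheduled times at the VASDHS". The Temporary COVID-19 Updates changed this: "We will use Cisco WebEx to conduct the remaining CM group therapy sessions and post-intervention sessions with the first participant cohort". Cohorts enrolled during the hold are also virtual. The study therapist "will review the previous 3 therapy sessions materials", which suggests, without saying so outright, that three sessions preceded the switch. The update then reports that "3 participants withdrew from the study because of lack of technology (devices and/or WIFI) necessary for virtual training sessions and data collection" and plans to mail them the post-intervention questionnaires, with their permission. It does not mention the completion rule.

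Two other provisions bear on the point. The CM intervention text runs the groups one after another so that each can reshape the next, and key question 4 in Section 6 asks what modifications are needed. The Analytic plan makes the primary analysis descriptive, names attendance among the things a class may influence, and provides for a random class effect and an intraclass correlation.

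**The concern.** One proportion now covers a cohort that changed format part-way through and cohorts that were virtual throughout, plus any in-person cohort run outside the hold (none is documented). If three sessions preceded the switch, nobody in the first cohort could reach six without at least three on WebEx, so that cohort measures neither in-person nor fully virtual completion. The three technology withdrawals, if they had started, fail the rule because of a disruption that a later trial would not repeat.

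The study exists to guide a larger trial, and whether older Veterans complete the intervention is among its first questions. A reader of the single rate could not tell how much non-completion came from the switch. The class effect and intraclass correlation describe clustering; they do not report completion by format or by reason for leaving.

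**Working it through.** **1. The plan's own figures.** The printed margin formula is 1.96 × p(1−p)/√n. At p = 0.60 it gives 0.4704/√30 = 0.086, 0.4704/√27 = 0.091 and 0.4704/√24 = 0.096, which match the stated completion margins. The formula lacks the square root over p(1−p). That is a separate matter, and those margins are not used as a yardstick here. The usual half-width, 1.96 × √(p(1−p)/n), is 0.175, 0.185 and 0.196 at p = 0.60, and 0.143, 0.151 and 0.160 at p = 0.80.

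**2. Does the rule leave the three withdrawals undecided?** There are two cases.
- Started CM and attended fewer than 6 sessions: in the completion denominator, not in the numerator.
- Consented but never started: outside the completion denominator, and counted against initiation.

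Every case is covered. What the documents do not state is a fact, namely whether each of the three had started. The session counts needed to apply the rule at all will supply it.

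**3. How much could the three matter?** Assume all three were CM starters, which is implied but not stated. The completer counts are illustrative. Half-widths are taken at p = 0.60 (first four rows) and p = 0.80 (last four).

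| n | Three counted | Three set aside | Shift | Half-width | Ratio |
|---|---|---|---|---|---|
| 30 | 18/30 = 0.600 | 18/27 = 0.667 | 0.067 | 0.175 | 0.38 |
| 27 | 16/27 = 0.593 | 16/24 = 0.667 | 0.074 | 0.185 | 0.40 |
| 24 | 14/24 = 0.583 | 14/21 = 0.667 | 0.083 | 0.196 | 0.43 |
| 20 | 12/20 = 0.600 | 12/17 = 0.706 | 0.106 | 0.215 | 0.49 |
| 30 | 24/30 = 0.800 | 24/27 = 0.889 | 0.089 | 0.143 | 0.62 |
| 27 | 22/27 = 0.815 | 22/24 = 0.917 | 0.102 | 0.151 | 0.68 |
| 24 | 19/24 = 0.792 | 19/21 = 0.905 | 0.113 | 0.160 | 0.71 |
| 20 | 16/20 = 0.800 | 16/17 = 0.941 | 0.141 | 0.175 | 0.81 |

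The shift is inside the half-width in every row. The half-widths ignore clustering by class; positive clustering would widen them and lower the ratios.

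Counting the three as non-completers caps the overall rate at 27/30 = 0.90, 21/24 = 0.875 or 17/20 = 0.85. If all three were in a first cohort of 8 to 10, it caps that cohort at 5/8 = 0.625 to 7/10 = 0.70. The plan's prior range for enrollment and completion is 0.57 to 0.82. The overall caps lie above that range and the cohort caps lie within it.

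**4. What would a split by format deliver?** Assume three groups, the later two both virtual, and p = 0.60.
- First cohort, n = 8 to 10: half-width 0.339 to 0.304.
- Later cohorts, n = 16 to 20: half-width 0.240 to 0.215.
- Difference between the two: 1.96 × √(0.24/8 + 0.24/16) = 0.416, down to 1.96 × √(0.24/10 + 0.24/20) = 0.372.

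A gap of less than about 37 to 42 points would not be distinguishable from chance. Any gap would also be confounded with cohort and with the planned changes to the manual. With only three in-person sessions held, no tabulation of the first cohort can produce an in-person completion rate.

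**The case for a change.** The strongest case for acting is that the addition costs a few table rows, matches the plan's descriptive approach, and would settle the presentation of the three withdrawals before anyone sees the results. The sequential adaptation of the manual was planned, whereas a forced change of format in mid-course was not. With two groups the shift is larger, 10.6 points near 0.60.

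Part of this stands. The rate does mix formats, nothing in the plan separates them, and a reader planning a later trial would want to see completion by cohort. The comparison with sampling error does not remove that point, because the effect of the switch is systematic.

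The case does not reach a change in the plan. The rate among all starters is what the plan set out to estimate, and it would remain primary under any version of the addition. The counting of the three is already fixed, so no later choice needs to be forestalled. Their number and reason for leaving are already on record, so the final report can state them. A rate that sets them aside would flatter virtual delivery, since lack of a device or connection is itself a barrier to it.

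**Conclusion.** The concern is right that the completion rate spans more than one delivery format, and that this narrows what it says about any single format. It does not show an error in the definition or the analysis. Followed as written, the plan yields a valid rate among all starters with a determinate place for the three withdrawals. Analysts can fill the remaining gap sensibly in the report by labelling each cohort's format and stating the start status and sessions attended of the three.

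On the assumption that all three were CM starters, the effect is 6.7 to 8.3 points near 0.60 and 8.9 to 11.3 points near 0.80 with 24 to 30 participants. With 20 participants it is 10.6 and 14.1 points. All are smaller than the correct 95% half-width. If any of the three had not started, the effect on completion is smaller and part of it moves to initiation. The by-format precision figures also assume three groups with both later groups virtual, which the documents do not confirm.
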